5.6 Consent Process

Subjects must give informed consent according to institutional review board (IRB) guidelines prior to registration. The subject will receive a copy of the signed consent document. The original signed consent document will be retained by the PRTBTC in a study binder. The PI or designee will fully explain the purpose and potential risks and benefits of the study to the subject prior to enrollment and address any questions posed by the subject. In addition, the PI or designee will explain to each subject the nature of the study, its purpose, the procedures involved, the expected duration, the potential risks and benefits involved and any additional discomfort that may be anticipated from taking this antiemetic drug combination. Each subject will be informed that participation in the study is voluntary and that he/she may withdraw from the study at any time and that withdrawal of consent will not affect his/her subsequent medical treatment or relationship with the treating physician.

The prospective participant will have as much time as he/she may need to make an informed decision about the study, and all treatment-related questions will be answered. Prospective participants will be consented in an exam room where only the research staff, the patient, and his/her family (if desired) are present. Before, during, and after the consent process, the research team and investigators will be available in person and by phone to answer any questions the participants may have. Any and all other available treatment options are

offered to the patient in order to avoid undue influence. Participants are not offered compensation for this study, in order to avoid any monetary coercion/influence.

For those prospective participants who cannot read or are blind, the consent document will be read out loud verbatim to the participant, who is encouraged to have a caregiver or family member present as a witness who can read along as the consent form is read. If the prospective participant cannot read or understand English, an approved, translated, short form consent document will be provided to the participant. A translator and a translator/witness, along with the Brain Tumor Center attending physician, nurse, or coordinator, will review the short form consent document and the full English version of the consent and all relevant study documents with the subject. If a subject has a physical impairment that limits their ability to provide a signature, an impartial witness will be utilized as part of the informed consent process. This impartial witness will date and sign the Informed Consent along with the person obtaining the informed consent.

5.7 Subject's Capacity to Give Legally Effective Consent

Subjects participating in this study are competent to sign informed consent, based upon inclusion criteria and investigator assessment. Subjects who do not have the capacity to give legally effective consent will not be enrolled.

5.8 Risk/Benefit Assessment

The natural progression of this type of brain tumor and standard treatment modalities are associated with potentially life-threatening complications and side effects. The antiemetic study drug (rolapitant) may increase the risk of side effects.

Table 1: The study of drug, Varubi® (rolapitant) with MEC can cause the following effects:

| | VARUBI Regimen (VARUBI, Dexamethasone, and 5-HT ₃ Receptor Antagonist) N = 670 | Control (Placebo, Dexamethasone, and 5-HT ₃ Receptor Antagonist) N = 674 |
|-------------------------|---|---|
| Decreased appetite | 9% | 7% |
| Dizziness | 6% | 4% |
| Dyspepsia | 4% | 2% |
| Urinary tract infection | 4% | 3% |
| Stomatitis | 4% | 2% |

Allergic reactions may occur rarely. Hives; tightness of the throat; difficulty breathing or swallowing; hoarseness should be reported to the study doctor immediately.

Note: The Reference Safety Information for the study will be the United States Package Insert (USPI).

Ondansetron

Most common side effects (occurring in 9 to 24% of subjects):

- Headache
- Fatigue
- Constipation

Side effects occurring in 5-6% of subjects:

- Diarrhea
- Dizziness

Other side effects that have been reported by people who have taken ondansetron (intravenous [by vein] or by mouth) in clinical studies include the following:

- Low oxygen level in the blood (Hypoxia)
- Fever
- Slow heart rate (Bradycardia)
- Urinary retention
- Itching
- Drowsiness/sedation
- Shivers

Serotonin syndrome has been reported when ondansetron has been taken at the same time as another medication that affects serotonin, a type of neurotransmitter (a chemical produced by the body). Such medications include certain types of anti-depressants and migraine medications. The study team will review your list of medications with you to find out if you are taking any of these medications. Please seek immediate medical attention if you experience any of the following symptoms of serotonin syndrome: changes in mental status, autonomic instability (this could include fainting or dizziness, exercise intolerance, sweating too much or too little, difficulty with urinating, sexual problems, and visual problems), neuro-muscular symptoms, and gastrointestinal symptoms, such as loss of appetite, bloating, diarrhea, constipation, or difficulty swallowing.

Other medications:

Subjects should tell the study doctor about all drugs that they have been taking recently and are taking while enrolled in this study. Also, if a severe side effect occurs, the study doctor may permanently stop the study drug. Subjects must tell their study doctor and research staff of their concern of any of these side effects, as listed above.

5.9 Costs to the Subject

The study drug, rolapitant, is FDA-approved and will be provided at no charge. Ondansetron is commercially available and will not be covered by the study. The subject or their third party insurance carrier will be responsible for the cost of his/her clinic visits, laboratory tests, dexamethasone (as needed), and the routine care and treatment of their brain tumor, e.g. the radiation therapy and temozolomide. How much one will have to pay, depends on whether or not the subject has insurance and those costs that his/her insurance will cover. Insurance coverage cannot be guaranteed for all tests and treatments related to this study. Treatment to help control any side effects that may occur may also result in added costs to the subject or their insurance company. Subjects will not be paid for taking part in this study.

5.10 Duration of Study

Participants will be in the study for 8 weeks which includes ~6 weeks of treatment and 2 weeks of monitoring for adverse events following the end of radiation and concurrent temozolomide treatment.

5.11 Data Analysis and Statistical Considerations

[figure not shown]
One hundred seventy (170) glioma patients will be enrolled with the expectation that 160 patients will be randomized (unblinded) to receive one of two treatment sequences of anti-emetic therapy for the prevention of nausea and vomiting associated with RT and concomitant TMZ. Sequence A involves a 3-week regimen of daily ondansetron followed by a 3-week regimen consisting of rolapitant (day 22 only) and daily ondansetron; whereas, Sequence B involves a 3-week regimen of rolapitant (day 1 only) and daily ondansetron followed by a 3-week regimen of daily ondansetron.

The primary endpoint of this study is CR rate. Though the primary CR rate endpoint will focus on treatment during the first 2 weeks of RT and TMZ, a cross-over design is proposed so that a patient will experience both modes of treatment, and be equipped to make a comparative assessment of preference, which is a key

secondary outcome. An interim analysis (as described in 15.6) will be conducted by the study statistician or designee after 40 patients are accrued to each sequence.

We expect that 152 of the 160 randomized patients to provide an assessment of their experience during the first 2 weeks of treatment with the first regimen. With 152 patients, there is 80% power to detect an increase in the CR rate from 75% with ondansetron to 90% with the combination of ondansetron and rolapitant (α =0.05; one-tailed) with a chi-square test.

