Changed Lead Regulatory Coordinator to [name]. Updated all references of Tesaro to TerSera, the new sponsor. Exclusion criteria #1 removed and combined with #2 to indicate that co-medication interaction with rolapitant will be reviewed by the pharmacist for eligibility and added exclusion criteria for contraindicated medications (Sections 5.4 and 11.2). Added a sentence after exclusion criterion 18 that says to refer to a study Memo to File for exceptions to the exclusion criteria. (Sections 5.4 and 11.2) Reordered the Inclusion and Exclusion criteria numbering to better lend itself to how the questions are reviewed when screening by the CRC. Removed collection of every 2 week standard of care blood draw at the request of the PI who determined it was unnecessary to collect the data (Table 7) and throughout the protocol. Section 13, Safety Monitoring and Reporting, was significantly revised to both include language suggested by the new sponsor TerSera and to remove sections that had only been included based on the previous sponsor's requirements. Corrected inconsistencies in the language related to screening time points. Removed overall duration of study. Other minor administrative changes.

The accrual target for this study is reduced to 57 patients. The decision to terminate early has not been influenced by the data collected to date, as no interim analyses have been conducted. The analyses as described below will be conducted; however, they may no longer have the power to detect the hypothesized effect size

| 1 | TA | BLE OF CONTENTS | |
|---|------|---|----|
| 2 | LI | ST OF FIGURES | 6 |
| 3 | LI | ST OF TABLES | 6 |
| 4 | LI | ST OF ABBREVIATIONS | 7 |
| 5 | PR | ROTOCOL SYNOPSIS AND RESEARCH SUMMARY | 8 |
| | 5.1 | Purpose | 8 |
| | 5.2 | Background and Significance | 8 |
| | 5.3 | Design and Procedure. | 9 |
| | 5.4 | Selection of Subjects | 10 |
| | 5.5 | Subject Recruitment and Compensation | 12 |
| | 5.6 | Consent Process | 12 |
| | 5.7 | Subject's Capacity to Give Legally Effective Consent | 13 |
| | 5.8 | Risk/Benefit Assessment | 13 |
| | 5.9 | Costs to the Subject | 14 |
| | 5.10 | Duration of Study | 14 |
| | 5.11 | Data Analysis and Statistical Considerations | 14 |
| 6 | ST | TUDY SCHEMA | 15 |
| 7 | BA | ACKGROUND AND SIGNIFICANCE | 16 |
| | 7.1 | Study Disease | 16 |
| | 7.2 | Study Agent | 16 |
| | 7.2 | 2.1 Pre-clinical experience (as noted in the Rolapitant Investigator's brochure) | 20 |

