Approximately 170 patients will provide informed consent in order for 160 patients to be randomized to either treatment sequence A or B. The 170 estimate is to allow for screen failures and dropout rates. All subjects must give written informed consent to participate in the study. Patients will be screened -28 to 0 days prior to the start of the study. During this time period the following information will be recorded: physical examination; vital signs and weight; laboratory studies (complete blood count with differential, blood chemistries, liver function tests and urinalysis): medical history; concomitant medications (steroids and anticonvulsants) and predictors of RINV (irradiation site, planned dose treatment field, alcohol intake, gender, age etc.). Laboratory evaluations, performance status, concomitant medications, and adverse events for final eligibility should be confirmed within 2 weeks of initiating radiation with concomitant TMZ

Patients will obtain standard of care blood work (per local oncologistduring treatment complete blood count with differential, blood chemistries, liver function tests). Toxicity will be assessed based on the Common Toxicity Criterion (CTC version 4). The patient will be asked to complete the MASCC nausea and vomiting questionnaire on day 0 (baseline), and days 1, 2, 4, and 7 (for days 7, 1, 2-3, and 4-6, respectively) of each week of radiation therapy.

At the end of weeks 3 & 6, the subject will be asked to fill out a Treatment Satisfaction Questionnaire for Medication (TSQM-9, Section 18.1 and 18.2) and will be asked at the end of week 6 to choose which antiemetic they prefer.

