Approximately 170 patients will provide informed consent in order that 160 patients be randomized to either treatment sequence A or B. The 170 estimate is to allow for screen failures and dropout rates. All subjects must give written informed consent to participate in the study. Patients will be screened -28 - 0 days prior to the start of the study. During this time period the following information will be recorded: physical examination; vital signs and weight; laboratory studies (complete blood count with differential, blood chemistries, liver function tests and urinalysis): medical history; concomitant medications (steroids and anticonvulsants) and predictors of RINV (irradiation site, planned dose treatment field, alcohol intake, gender, age etc.). Laboratory evaluations, performance status, concomitant medications, and adverse events for final eligibility should be confirmed within 2 weeks of initiating radiation with concomitant TMZ. Patients will obtain standard of care blood work (per local oncologist) (complete blood count with differential, blood chemistries, liver function tests). Toxicity will be assessed based on the Common Toxicity Criterion (CTC version 4). The patient will be asked to complete the MASCC Antiemesis Tool (MAT- see appendices) nausea and vomiting questionnaire on day 0 (baseline) and days 1, 2, 4, and 7 of each week of radiation therapy. In addition, they will be asked to record their use of any antiemetic rescue medication.

At the end of weeks 3 & 6, the subject will be asked to fill out a Treatment Satisfaction Questionnaire for Medication (TSQM-9- see appendices) and will be asked at the end of week 6 to choose which antiemetic they prefer.

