15.4 Primary Objective

The primary objective of this study is to compare the efficacy of rolapitant plus ondansetron vs. ondansetron alone in the prevention of nausea and vomiting, as measured by the overall complete response rate, among malignant glioma patients during RT and concomitant TMZ (see Section 8).

As described in Sections 15.6 and 15.7, the study was originally designed to enroll 170 glioma patients with the expectation that 160 patients would be randomized to receive one of two treatment sequences of anti-emetic therapy for the prevention of nausea and vomiting associated with RT and concomitant TMZ. A formal interim analysis was planned after 80 patients had been randomized (i.e. 40 patients to each treatment sequence). As of mid-January 2022, 53 patients had been randomized. On January 18, 2022, TerSera, the study's funding source, requested that accrual to the study be terminated in the next few months.

Given this request from TerSera, the accrual target for this study is reduced to 57 patients. The decision to terminate early has not been influenced by the data collected to date, as no interim analyses have been conducted. The analyses as described below will be conducted; however, they may no longer have the power to detect the hypothesized effect size.

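### Sections 5.3, 5.11 and 9.1 still state the 160-patient design, and 5.11 an interim look and 80% power; at the current 57-patient target, power for 75% vs 90% is about 44%, a figure the plan does not state

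*Combined protocol and SAP*

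**What the plan says.** Three sections describe the larger trial in the present or future tense, with no sign that the design has been superseded:

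- Section 5.3: "Approximately 170 patients will provide informed consent in order for 160 patients to be randomized to either treatment sequence A or B".
- Section 9.1: "Approximately 170 patients will provide informed consent in order that 160 patients be randomized to either treatment sequence A or B".
- Section 5.11: "One hundred seventy (170) glioma patients will be enrolled with the expectation that 160 patients will be randomized (unblinded" to one of the two sequences. It continues: "An interim analysis (as described in 15.6) will be conducted by the study statistician or designee after 40 patients are accrued to each sequence". It then says: "With 152 patients, there is 80% power to detect an increase in the CR rate from 75% with ondansetron to 90" percent with the combination, at one-tailed alpha 0.05 with a chi-square test.

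Elsewhere the plan describes a smaller trial. The front matter says: "The accrual target for this study is reduced to 57 patients". Section 15.4 reports: "As of mid-January 2022, 53 patients had been randomized". It then explains that the funder asked for accrual to end, and that "the accrual target for this study is reduced to 57 patients". Both places warn that the planned analyses might lack power for the hypothesised effect. Section 15.6 keeps the interim under an original-design label and says that none is planned under the modified design. Section 15.7.2 gives 80% power with 57 patients for 75% vs 97%, or alternatively for 63% vs 90%.

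**The concern.** The two sets of statements cannot both describe the trial as it now stands. The size in 5.3, 5.11 and 9.1 conflicts with 15.4 and 15.7.2. The interim in 5.11 conflicts with 15.6, the section it cites, and it needs 80 patients, which a target of 57 never reaches. This is a conflict within current text, not a difference between current text and a change log.

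The power statement matters most. The effect the trial was designed to detect is a rise in CR rate from 75% to 90%. The document attaches one power to that effect, 80% (in 5.11 and 15.7.1). Section 15.7.1 labels it as original design, but 5.11 does not. Someone who reads only the synopsis, or who later interprets a non-significant primary result, could take the trial to be adequately powered for its hypothesised effect when its power is below one half.

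**Working it through.** **Inputs.** CR rates p0 = 0.75 and p1 = 0.90, one-tailed alpha 0.05 and a chi-square test (5.11). Allocation 1:1 (9.6). Patients: 152 (5.11) and 57 (15.4, 15.7.2). Section 15.4.2 names a chi-square test for the primary analysis but gives neither sidedness nor whether a continuity correction is used. The one-tailed setting comes from the power text.

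**Formula** (normal approximation, pooled variance under the null, n per arm, pbar = (p0 + p1)/2):

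power = Φ{ [ (p1 − p0)√n − 1.645·√(2·pbar·(1 − pbar)) ] / √(p0(1 − p0) + p1(1 − p1)) }

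For 75% vs 90%:

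- pbar = 0.825
- √(2 × 0.825 × 0.175) = 0.5374, and 1.645 × 0.5374 = 0.884
- √(0.1875 + 0.0900) = 0.5268

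**1. Reproduce the stated 80% at 152 (n = 76).** 0.15 × √76 = 1.308. (1.308 − 0.884)/0.5268 = 0.80, so power is 78.9%. Exact enumeration of the same uncorrected test gives 80.4%. The stated figure reproduces. Other versions do not match it at 152: exact enumeration of a continuity-corrected or Fisher test gives 73.6%, and a two-sided test gives 68.5% (normal) or 70.3% (exact).

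**2. Check the 15.7.2 figures at 57 (n = 28.5).** The exact ranges cover the 28/29 and 29/28 splits.

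| Comparison | Pooled normal | Exact, uncorrected | Stated |
|---|---|---|---|
| 75% vs 97% | 78.5% | 83.9-85.5% | 80% |
| 63% vs 90% | 78.8% | 80.3-81.7% | 80% |

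Both statements are consistent with the same one-sided, uncorrected method.

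**3. Power for 75% vs 90% at 57.** 0.15 × √28.5 = 0.801. (0.801 − 0.884)/0.5268 = −0.158, so power is 43.7%.

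| Version, 57 patients | Power |
|---|---|
| One-sided, uncorrected, pooled normal (28/29 or 29/28) | 43.5-43.9% |
| One-sided, uncorrected, exact | 44.8-45.8% |
| One-sided, continuity-corrected or Fisher, exact | 31.1-32.1% |
| Two-sided, uncorrected | 31.6% (normal, n = 28.5), 32.5-33.8% (exact) |

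**4. Sensitivity to assessability.** The modified design states no assessable share. Assuming the original share, 57 × 152/160 = 54.2. With 27 per arm, one-sided and uncorrected, power is 42.1% (normal) or 44.3% (exact).

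**5. Interim.** 40 per sequence × 2 = 80, which exceeds 57.

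**The case against.** The strongest reply is that the plan deals with this where the analysis is governed. The front matter announces 57 and warns about power. Section 15.4 dates and explains the cut, and 15.6 and 15.7 separate the original from the modified design. The interim sentence in 5.11 sends the reader to 15.6, where the interim is withdrawn. With 53 of 57 already randomised by mid-January 2022, nobody is likely to recruit to 160 or run the interim. Most of this stands, and it limits the practical harm. It does not reconcile three unlabelled sections with section 15.

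A reader might go further and infer that the plan hides the loss of power, or gives no means of judging it. The documents do not support that. Section 15.7.2 expresses the loss as a detectable difference: 22 points (75% vs 97%) or 27 points (63% vs 90%), against 15 points in the original design. That is a legitimate way to report reduced power. What is missing is narrower: the power at the hypothesised effect.

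A reader might also infer that the 80% is a calculation error. It is not, since it is right for 152 patients. Nor is there good reason to suspect that 57 counts consented rather than randomised patients: 15.4 sets it directly after reporting 53 randomised, and 15.7.2 uses it as the number for power.

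One further objection stands in full. The documents say only chi-square, so the absence of a continuity correction is inferred from the figure that reproduces. The 44% must therefore be given with its conditions.

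**Conclusion.** The point holds as an incomplete update. The size in 5.3, 5.11 and 9.1, and the interim and power in 5.11, are not those of the current design. For 75% vs 90% with 57 patients, power is about 44% (43.5-45.8%), against the 80% that 5.11 still gives. This rests on a one-sided 0.05 chi-square test without continuity correction and on all 57 being assessable. With 54 assessable, an assumption, it is about 42-44%. If the test were instead two-sided, or continuity-corrected or Fisher (each change taken alone), it would be about 31-34%. Because the reduction is disclosed and the detectable differences at 57 are given, this should be fixed but does not invalidate the analysis.

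**What to change.** - **5.3, 5.11 and 9.1:** replace 170/160 with the 57-patient target, or label those figures as the original design, as 15.6 and 15.7 already do.
- **5.11:** label the interim and the 80% power with 152 patients as original design, and state that no interim is planned.
- **15.7.2:** add that power for the originally hypothesised 75% vs 90% with 57 patients is about 44% (one-sided alpha 0.05, chi-square without continuity correction), and about 31-34% if the test is two-sided, continuity-corrected or Fisher.

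The cost is wording in four sections. Patients, endpoint, test and analysis set do not change. The downside is that the stated power for the hypothesised effect becomes less favourable.

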6 STUDY SCHEMA

7 BACKGROUND AND SIGNIFICANCE

7.1 Study Disease

Radiation-induced nausea and vomiting (RINV) is a clinically distressing symptom in patients undergoing radiotherapy. The RINV risk in patients receiving cranial/craniospinal radiation without concurrent chemotherapy is estimated to around 30-60%.1 Although there is limited evidence to suggest what the RINV incidence is higher with the addition of temozolomide to RT than without, one would only predict that the addition of concurrent chemotherapy with brain irradiation would only increase the RINV rate. In two recent clinical studies, 35% or more of cranial RT patients experienced RINV.^{2,3} The risk of RINV increases when concomitant chemotherapy with TMZ is added to brain RT,⁴ as TMZ is moderately emetogenic.^{5,6} Temozolomide prescribing information reports nausea and vomiting rates of 36% and 20% respectively for concomitant RT+TMZ and concomitant RT+TMZ with standard antiemetic treatment. Comparable rates of nausea (35%) and vomiting (26%) were reported in a recent study of Korean malignant glioma patients receiving such treatment.8 The National Comprehensive Cancer Network (NCCN), Multinational Association of Supportive Care in Cancer (MASCC), and American Society of Clinical Oncology (ASCO) publish current clinical practice guidelines addressing the issue of RINV 9,10,6 These guidelines recommend that patients receiving concomitant chemotherapy and RT treatment should be given antiemetic prophylaxis according to the emetogenicity of the chemotherapy prescribed, unless the emetic risk of the radiotherapy is higher. Given the moderate emetogenicity of TMZ therapy, patients with brain tumors are classified as a moderate-risk group for RINV.

At Duke PRTBTC, we estimate the RINV rate to be approximately 50% without the use on ondansetron. Despite prophylaxis against nausea and vomiting during cranial RT and concomitant temozolomide therapy, Stupp ^{4,11} reported a threefold (14% - 40/287) increase in the grade 2-4 nausea/vomiting rate compared to a 4% (11/286) nausea/vomiting rate with radiotherapy alone. Without prophylaxis, up to 60% of patients receiving cranial radiation may experience acute nausea and vomiting, which can lead to various adverse effects including dehydration, electrolyte imbalance, malnutrition, and aspiration pneumonia. These complications can further delay/decrease the therapeutic effect of temozolomide and radiation treatment, ultimately leading to lower response rates and decreased health-related quality of life (HRQoL).

We conducted the first phase 2 single arm trial of palonosetron (PAL), a long acting 5-hydroxytryptamine (5-HT₃) receptor antagonist (5HT₃-RA), for the prevention of RINV in primary MG subjects receiving RT (54-60 Gy) and concomitant multi-dose, daily TMZ (75 mg/m²) +/- bevacizumab. Results from this study demonstrate that a 5HT₃-RA, such as PAL or ondansetron, can be safe and effective, however based on the results, there is still room for improvement of anti-emetic response related to CR rates and HRQoL, which could be addressed by combining a 5-HT₃-RA and NK-1-RA¹². PAL was safe and effective; however, there is room for improvement in the CR rates and HRQoL, which may be achieved with rolapitant plus ondansetron, a potentially more effective combination anti-emetic regimen. Additionally, PAL is only available as an IV injection in the United States whereas ondansetron can be administered orally, making it a more patient-friendly drug. The most studied agents in the RINV settings are the 5HT₃-RAs, with overall moderate response and low toxicity. However, agents such as the tachykinin NK-1 receptor antagonist may play a role in improving response rates, but there needs to be further studies in randomized controlled trials.¹³

